Appendix 1 summarizes the standard evaluation procedures.

Table 1. Visits and Study Assessments

Study Assessments	Visit 1 Preoperative	Visit 2 Operative	Visit 3 Day 1	Visit 4 Day 15 ±2	Visit 5 Day 30 ±5
Inclusion/Exclusion Criteria	x				
Consent Subject	x				
Patient demographics (age, gender, race, ethnicity)	x				
Manifest Refraction	x		x	x	x
UCDVA	x		x	x	x
BCDVA	x			x	x
Goldman Tonometry (IOP)	x		x	x	x
Complete slit lamp exam	x		x	x	x
Dilated fundus exam	x				†
Cataract density	x				
Ultrasonic central corneal pachymetry	x		x	x	x
Central macular thickness (OCT)	x			x	x
Use of femtosecond laser		x			
Phacoemulsification time		x			
CDE		x			
Estimated fluid used		x			
Duration of surgery		x			
Record Lens Model Implanted		x			
Patient satisfaction					x
Symptoms (FBS & burning/stinging)	x		x	x	x

Pain	x		x	x	x
Adverse events / device deficiency		x	x	x	x

x To be performed as scheduled

† To be performed as deemed necessary by the investigator.

4. Study Completion Criteria

- 4.1. Patient Completion of Study: If a study patient has completed the final visit (Visit 5) of the study, he/she is considered to have completed the study.
- 4.2. Patient Discontinuation/Withdrawal: Each study patient may voluntarily discontinue the study at any time they choose. Study patients who cannot complete the study for administrative reasons (e.g., non-compliance, failure to meet visit schedule, etc.) will be discontinued from the study. Study patients discontinued during the enrollment phase (prior to surgery) of the study will be replaced.
- 4.3. Patient Termination: A study patient will be terminated if the study patient develops any severe adverse event that may be related to the study. A study patient will receive appropriate treatment at the discretion of the investigator. Notification of termination will be clearly documented. These study patients are considered to have completed the study and will not be replaced.
- 4.4. Study Termination: The investigator with appropriate notification may terminate the study. If, after clinical observations, the investigator feels that it may be unwise to continue the study, he may stop the study.
- 4.5. Study Completion: The study will be complete when all enrolled patients have completed Visit 5 or have been terminated from the study.

5. STATISTICAL CONSIDERATIONS

5.1. Sample size

We estimate that the ability of the Cirrus OCT to measure changes in macular thickness has a standard deviation around 6 microns. For sample size calculation we set the statistical significance to $\alpha = 0.05$ with a power (beta) of 0.9. Using a dependent model, detecting a 5 micron difference in the change in retinal thickness between eyes is estimated to require 30 subjects. To allow for 15% dropout, 35 subjects will be enrolled.

5.2. Statistical Analysis

All data will be collected by the site and entered into a database. Subjects will be assigned an ID number. Data analysis will be performed without patient identification. Statistical analysis will be performed using standard descriptive statistics and other tests as deemed appropriate based on the characteristics of the data to be analyzed. All statistical tests will be two-sided and interpreted at a 5% significance level. Comparisons between the groups will be made. Data analysis will be conducted by a third party consultant.

5.3. Study Endpoints:

Comparisons between the groups:

5.3.1. Primary Endpoints:

- Change from baseline (preoperative exam) in macular thickness at Days 15 \pm 2 and 30 \pm 5.

5.3.2. Secondary Endpoints:

- The change from baseline in corneal thickness at Day 1, Day15 \pm 2, and Day 30 \pm 3.
- Slit lamp (cornea exam) changes at all times points.
- The proportion of subjects reporting no eye pain/discomfort (“0” on the eye pain/discomfort) at all time points.
- The change from baseline in eye pain/discomfort score at all time points.
- The proportion of subjects reporting FBS (“0”) at all time points.
- The change from baseline in FBS at all time points.
- The proportion of subjects reporting burning/stinging (“0”) at all time points.
- The change from baseline in burning/stinging at all time points.
- The proportion of subjects with a corneal pachymetry change from baseline at all time points.
- The change from baseline in corneal pachymetry measurements at all time points.
- The proportion of subjects with patient satisfaction score of 3 or higher at Day 30 visit.

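### Every test is read at 5% across eleven unranked secondary endpoints, one of them an exact repeat, so the chance of at least one nominally significant secondary result is well above 5% even if the regimens do not differ

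*Combined protocol and SAP*

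**What the plan says.** Section 5.2 gives one decision rule for the whole study: "All statistical tests will be two-sided and interpreted at a 5% significance level". It names no test for any efficacy endpoint and allows descriptive statistics and "other tests as deemed appropriate based on the characteristics of the data to be analyzed".

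Section 5.3, introduced as comparisons between the groups, has one primary endpoint (change in macular thickness, at Days 15 and 30) and eleven secondary bullets. Nothing in 5.2 or 5.3 ranks the bullets, adjusts for their number or calls them supportive or descriptive.

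Three bullets concern corneal thickness:
- "The change from baseline in corneal thickness at Day 1", and at Days 15 and 30;
- "The proportion of subjects with a corneal pachymetry change from baseline at all time points", with no threshold for what counts as a change;
- "The change from baseline in corneal pachymetry measurements at all time points".

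Table 1 and item 6 of the standard evaluation procedures in Appendix 1 describe a single corneal thickness measurement, ultrasound pachymetry, taken preoperatively and at Days 1, 15 and 30. The first corneal bullet gives Day 30 a window of ±3 days. Section 3.3.1, Table 1 and the primary endpoint use ±5.

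Pain, foreign body sensation and burning/stinging each appear twice, once as a proportion (for pain, "The proportion of subjects reporting no eye pain/discomfort") and once as a change in score ("The change from baseline in eye pain/discomfort score at all time points"). Section 5.4 adds a Fisher's exact comparison of adverse-event proportions.

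**The concern.** A sentence covering all tests makes any secondary p-value below 0.05 a significant result by the plan's own standard. The label of secondary does not override it. With many comparisons and no order among them, a few such results can arise by chance, and nothing in the plan says how to read them.

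Two features make this matter more here. The exact repeat, together with the paired proportion and score versions of each symptom, lets one chance imbalance show up as two or more findings. Also, most of the comparisons concern comfort (three symptoms x two forms x three visits = 18), and the introduction already suggests comfort as an advantage of the combined drop. A difference at one visit could therefore be read as a demonstrated benefit.

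**Working it through.** The plan states no number of comparisons and no error rate across them, so there is no figure to reproduce. The sample size in 5.1 rests on macular thickness alone and is not affected.

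**Inputs from the documents.** Two-sided 5% level (5.2); eleven secondary bullets (5.3.2); three postoperative visits at which pachymetry, slit lamp, symptoms and pain are assessed (Table 1); satisfaction compared at Day 30 only (5.3.2); 30 subjects after dropout (5.1).

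**Assumptions.** One test per bullet per visit. The documents give no correlations between tests, so a range is used.

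**Step 1: count.** Ten bullets x 3 visits + 1 = 31. The two continuous corneal bullets are the same quantity, so removing one leaves 31 − 3 = 28. Testing stromal and epithelial edema separately (both are graded in Appendix 1) would add 3.

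**Step 2: expected number if the regimens do not differ.** k × 0.05, whatever the correlation, if every test has a true size of 5%:
- 31 tests: 1.55
- 28 tests: 1.40

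**Step 3: chance of at least one if independent.** 1 − 0.95^k:
- 28 tests: 1 − 0.95^28 = 0.762
- 31 tests: 1 − 0.95^31 = 0.796. The rise from 0.762 is an artefact, because an exact repeat cannot add a new chance of error.

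**Step 4: allowing for correlation.** Simulated two-sided z-tests, 28 tests, one common correlation:

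| Assumed correlation | P(at least one p < 0.05) |
|---|---|
| 0 | 0.76 |
| 0.3 | 0.64 |
| 0.5 | 0.49 |
| 0.7 | 0.33 |

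Simulations with correlation structured by measure, visit and symptom gave 0.70 (weak), 0.62 to 0.63 (moderate), 0.53 (strong) and 0.42 (very strong).

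**Step 5: allowing for discrete tests.** Of the 28, 13 are proportions (4 bullets x 3 visits + satisfaction) and 15 are not. The plan names no test for the proportions. If exact McNemar tests on 30 pairs are assumed, the true size is about 0.2%, 1.3%, 2.1% and 2.4% at 10%, 20%, 30% and 40% discordant pairs. At the two ends:
- expected number: 15 × 0.05 + 13 × 0.002 ≈ 0.8, to 15 × 0.05 + 13 × 0.024 ≈ 1.1
- chance of at least one, if independent: 1 − 0.95^15 × 0.998^13 ≈ 0.55, to 1 − 0.95^15 × 0.976^13 ≈ 0.66

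So 1.4 is close to an upper bound for 28 tests, and correlation would lower the 0.55 to 0.66 further.

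**Step 6: the primary endpoint.** It has two visits and no rule for combining them. If success at either visit at 5% sufficed, the error rate would be 1 − 0.95² = 9.75% under independence. Any instruction that refers to the primary succeeding needs that rule first.

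**The case against.** The strongest reply is that the documents never commit to 28 or 31 tests. Section 5.2 allows descriptive statistics, so some bullets may only be summarised, and one repeated-measures test per endpoint would also fit the text. Counting only distinct measures (corneal thickness, slit lamp, pain, foreign body sensation and burning at three visits, plus satisfaction) gives 5 × 3 + 1 = 16 tests, 0.8 expected and 1 − 0.95^16 = 56% under independence. These points stand: the count is an inference, and the size depends on it. Even so, 56% is far from 5%.

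It can also be said that unadjusted secondary endpoints are common in a single-site study of 35 subjects, that these are already labelled secondary, and that no passage makes one of them grounds for declaring success. That stands too, and it makes this a matter of interpretation that leaves the primary result untouched. It does not answer the sentence in 5.2, which sets a significance rule for every test done.

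A reader might infer three stronger things that the documents do not support:
- **That 1.55 false positives and an 80% chance are firm rates.** Both include the exact repeat, and the 80% also assumes independence.
- **That a chance finding is more likely than not.** This depends on the correlations, which are not given; at a common correlation of 0.5 the figure is already just under one half.
- **That formal adjustment of all secondary endpoints is needed.** No claim is planned on them, so supportive labelling is enough.

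**Conclusion.** The point holds as a cheap improvement. The plan states a 5% rule for all tests over eleven unranked secondary endpoints, with one corneal quantity entered twice and a responder form of it entered once more. Following it as written allows chance differences to be called significant.

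The size, for 28 distinct comparisons and no difference between regimens, is at most about 1.4 nominally significant results expected. The chance of at least one is about 76% under independence, down to about 33% at a common correlation of 0.7. Exact paired binary tests would reduce this further. These figures rest on one test per bullet per visit and on assumed correlations, so they show a range and are not an error rate for this trial. The conclusion does not depend on the exact value: over the range considered, the chance is several times 5%.

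**What to change.** In 5.2:
- Limit the 5% significance claim to the primary endpoint, and state how its Day 15 and Day 30 results are handled, for example one named visit as primary, or both required.
- State that the 5.3.2 endpoints and the adverse-event comparison in 5.4 are supportive. Report them as estimates (paired between eyes for 5.3.2) with 95% confidence intervals and nominal p-values, without a claim of significance.

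In 5.3.2, keep a single entry for change in corneal thickness, and give it one Day 30 window that agrees with the visit schedule.

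The cost is a few sentences and one deleted bullet. Data collection, visits and sample size do not change. The downside is that fewer secondary results may be called significant.

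### Macular thickness change is primary at both Day 15 and Day 30 with no rule for success; if either visit is enough, the false-positive rate is about 7% to 10%, not 5%.

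*Combined protocol and SAP*

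**What the plan says.** - **Section 5.3.1**, under a plural heading, has one bullet: "Change from baseline (preoperative exam) in macular thickness at Days 15" and 30, each with its visit window. Table 1 and Appendix 1 (item 5) schedule postoperative OCT at exactly these two visits, so there will be two primary comparisons.
- **Section 5.2** sets the level for each test: "All statistical tests will be two-sided and interpreted at a 5% significance level". For method it offers descriptive statistics and "other tests as deemed appropriate based on the characteristics of the data to be analyzed".
- **Section 5.1** plans for one comparison. At alpha 0.05 and "with a power (beta) of 0.9", it states that "detecting a 5 micron difference in the change in retinal thickness between eyes is estimated to require 30 subjects". No visit is named.
- The only test named anywhere is Fisher's exact test, for adverse events (Section 5.4).

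The documents contain no lead visit, testing order, either-or-both rule, joint or repeated-measures test, or multiplicity adjustment for the primary endpoint.

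**The concern.** Three success rules fit the text, and they behave differently. If a significant result at either visit counts, two unadjusted 5% tests give an overall false-positive rate above 5%. If both visits must be significant, the error rate is held but power drops below that of the single comparison in Section 5.1. One joint test over both visits would also hold 5%, but none is named.

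The documents do not say that either visit is enough; equally, nothing excludes it. The rule can be chosen once both results are known, and a reader of the final report could not tell which rule had been intended.

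**Working it through.** **Inputs.** From Section 5.1: difference 5 µm, SD 6 µm, alpha 0.05, power 0.9, 30 subjects. From Section 5.2: two-sided tests at 5%. From Section 5.3.1: two visits. Assumed, because the documents do not give it: the correlation r between the Day 15 and Day 30 between-eye differences.

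**Reproducing the plan's 30.** Taking 6 µm as the per-eye SD with independent eyes, the between-eye SD is 6 × √2 = 8.49 µm. The paired normal formula gives

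n = ((1.960 + 1.282) × 8.49 / 5)² = 30.26,

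which matches the stated 30. If 6 µm were already the SD of the between-eye difference, the same formula would give 15.13, or 16 subjects. The power figures below therefore use 8.49 µm. With 30 pairs, a two-sided paired t-test at 5% has 87.7% power at one visit (89.8% by the normal approximation).

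**Error rates with no true difference at either visit.** With Z₁ and Z₂ bivariate normal with correlation r:

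- either visit: 1 − P(|Z₁| < 1.96 and |Z₂| < 1.96)
- either visit, counting only results that favour the combination drop: P(Z₁ > 1.96 or Z₂ > 1.96); at r = 0 this is 2 × 0.025 − 0.025² = 4.94%
- both visits: P(|Z₁| > 1.96 and |Z₂| > 1.96)

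| r | Either visit | Either visit, favourable only | Both visits |
|---|---|---|---|
| 0 | 9.75% | 4.9% | 0.25% |
| 0.5 | 9.07% | 4.5% | 0.93% |
| 0.8 | 7.81% | 3.9% | 2.19% |
| 0.9 | 7.04% | 3.5% | 2.96% |

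The first and last columns sum to 10%, as they must for two 5% tests. For a single visit the figures are 5% (either direction) and 2.5% (favourable only). Above r = 0.9 the either-visit rate keeps falling: 6.46% at 0.95 and 5.66% at 0.99. Simulated paired t-tests with 30 pairs gave 9.7%, 9.1%, 7.8% and 7.1% for the either-visit column.

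Under the both-visit rule, if one visit has a large effect (15 µm simulated) and the other none, the error rate rises to 5.0%; it does not go above that.

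**Power with 5 µm at both visits** (30 pairs, SD 8.49 µm, paired t, simulated; one visit alone is 87.7%):

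| r | Both visits significant | Holm, a given visit | Second visit significant, first not |
|---|---|---|---|
| 0 | 76.9% | 86.2% | 10.8% |
| 0.5 | 79.7% | 85.2% | 8.1% |
| 0.8 | 82.4% | 84.2% | 5.2% |
| 0.9 | 84.0% | 83.7% | 3.8% |

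**Power with 5 µm at one visit only.** Holm claims that visit in about 80% of trials. A fixed order that puts the other visit first claims it in 3.8% (r = 0.5) or 3.1% (r = 0.8).

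**The case against.** The strongest reply is that the plan never adopts an either-visit rule, so 7% to 10% describes the most permissive of several readings. That is true, and the figure is conditional. What is established is a missing decision rule. The inflation is what the omission permits.

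Second, both changes are measured from the same preoperative scan, which ties them together. With equal variances and equal correlations across the three time points, the two changes correlate at 0.5, so r = 0 is unlikely and the top of the range is a bound. This stands, but it trims little: the rate is 9.1% at r = 0.5 and still 7.0% at r = 0.9.

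Third, the background speaks of comparable results for combination drops. If the aim were to show similarity, extra findings of a difference would work against the sponsor. But no margin or equivalence hypothesis is stated, Section 5.1 plans to detect a difference, and a similarity claim would also need a rule on which visit decides.

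Fourth, the power figures rest on one reading of the SD. If 6 µm is the SD of the between-eye difference, 30 pairs give 99.3% power at one visit and about 98.6% to 99.0% for both, so the loss nearly vanishes. This limits the power argument. It does not touch the error rates, which do not depend on the SD.

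**Conclusion.** The point holds and should be fixed. Section 5.3.1 sets two primary comparisons, Section 5.2 reads each at 5%, and nothing says how they combine. On an either-visit reading the two-sided false-positive rate is about 7% to 10% for between-visit correlations from 0.9 down to 0, moving towards 5% only as the correlation nears 1. On a both-visit reading the error rate is controlled, and power at 30 pairs is about 77% to 84% against 87.7% for one visit, given a between-eye SD of 8.49 µm. The correlation and that SD are assumptions. The absence of a rule is plain from the text. The data remain usable, provided the rule is fixed before the outcome data are analysed.

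**What to change.** Before the outcome data are analysed, state one rule in Section 5.3.1.

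**Option 1, if the sponsor has a reason to prefer one visit.** Suggested text: *The primary endpoint is the between-eye difference in change from baseline in macular thickness at [one visit, sponsor's choice], tested by a two-sided paired t-test at 5%. The other visit is tested in the same way at 5% only if the first is significant.*

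**Option 2, if it has no such reason.** Use Holm across the two visits: compare the smaller p-value with 2.5% and, if it passes, the other with 5%.

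Under either option, report the estimate and 95% confidence interval at both visits whatever the tests show.

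**Cost.** Stating the rule takes one or two sentences and no extra visits. The rest of the cost is in power (30 pairs, SD 8.49 µm):

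- Fixed order keeps 87.7% at the lead visit, but the second visit can never be claimed alone. With 5 µm at both visits, that forgoes a significant second visit in 8.1% of trials at correlation 0.5 and 5.2% at 0.8. If only the second visit has the effect, it is claimed in 3.8% of trials (correlation 0.5).
- Holm lowers power for a given visit to about 84% to 86% if both visits have the effect, and to about 80% if only that one does. It is the safer choice when no visit is clearly preferred. Neither option requires more patients to hold the 5% level. But if the sponsor wants 90% power at a single visit tested at 2.5%, that takes 36 pairs by the normal approximation or 39 by the paired t-test, before dropout, against the planned 30.

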4. **Anterior Chamber Cells and Flare:** Postoperatively at day 1, 15 and 30, anterior chamber cells and flare will be evaluated before tonometry or any other test that would affect examination. Both will be graded by the examiner using the following scale:

Number of Cells	Flare
0- none	0- none
1 - 1-5 cells	1 - Tyndall effect barely discernible
2 - 6-15	2 - mild Tyndall effect
3 - 16-30	3 - strong Tyndall effect
4- > 30	4 - intense Tyndall effect - aqueous has milky white appearance

5. **Macular thickness** (preop, days 15 and 30): It will be measured before tonometry or any other test that would affect OCT measurements. Macular thickness will be performed using SD-OCT (Cirrus [Zeiss]) following the manufacturer's recommendations. One 512 x 128 Macular Cube scan will be acquired per eye.
6. **Central corneal ultrasound pachymetry:** To be measured preop, and at day 1, 15 and 30. Three measurements will be taken and recorded as well as the average of the 3 measurements taken.

- 7. Intraocular pressure measurements:** IOP measurements will be measured at the Screening visit and at day 1, 15 and 30 postoperatively using Goldmann tonometry.
- 8. Questionnaires:** Examiner will read aloud the questions to the subject and will record the response given by the subject in the source document. For the Visual Analog Scale (VAS), the examiner will ask the patient to place a vertical mark on the line for each question then use ruler (cm) to calculate the score with 1 mm equal to 0.1 cm. A decimal value should be recorded (i.e., 2.1, 4.0). Questions 4 to 6 will be asked only at the Day 30 visit.
- 9. Dilated fundus examination:** To be performed preoperatively and at Day 30 (if deemed necessary by the investigator) using the investigator's preferred technique.

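### The primary comparison of change in macular thickness has no pre-specified adjustment for the preoperative between-eye difference, a low-cost precision gain whose size depends on an unstated correlation

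*Combined protocol and SAP*

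**What the plan says.** Section 5.3.1 gives the primary endpoint as "Change from baseline (preoperative exam) in macular thickness at Days 15" (±2) and 30 (±5). Section 5.1 bases the sample size on "detecting a 5 micron difference in the change in retinal thickness between eyes", under a paired model with no covariate term.

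Section 5.2 names no test, model or covariate for this endpoint: "Statistical analysis will be performed using standard descriptive statistics and other tests as deemed appropriate based on the characteristics of the data to be analyzed". It does fix sidedness and level: "All statistical tests will be two-sided and interpreted at a 5% significance level".

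Table 1 and Appendix 1, item 5, schedule OCT preoperatively and at Days 15 and 30. On acquisition, Appendix 1 says: "One 512 x 128 Macular Cube scan will be acquired per eye". Section 3.3.2 randomises the treatment of the first operated eye, with equal numbers of first eyes on test and control.

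**The concern.** A change score fixes the coefficient of the baseline at 1. A regression on baseline estimates that coefficient from the data. When baseline and follow-up are less than perfectly correlated, as with a single scan per visit that carries measurement error, a coefficient of 1 over-corrects and adds variance.

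The contralateral design removes differences between patients. It does not remove the difference between one patient's two eyes before surgery. That difference is measured for every patient and could serve as the covariate. With about 30 evaluable pairs, any avoidable variance matters for power or for the width of the confidence interval.

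**Working it through.** **Inputs from the documents.** Section 5.1 gives a 5 micron difference, an SD of around 6 microns, two-sided 5% significance, 90% power, 30 subjects and 35 enrolled. Section 5.1 describes the SD this way: "We estimate that the ability of the Cirrus OCT to measure changes in macular thickness has a standard deviation around 6 microns". It does not say whether 6 microns is the SD of one eye's change or of the between-eye difference in change.

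**Reproducing the plan's N.** The paired normal formula is n = ((1.960 + 1.282) × SD_diff / 5)².
- 6 microns per eye, eyes uncorrelated: SD_diff = 6 × √2 = 8.49, n = 30.26. This rounds up to 31, close to the stated 30. The paired t calculation gives 33.
- 6 microns already the between-eye SD: n = 15.13, rounding up to 16. The paired t calculation gives 18.

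The first reading roughly reproduces the plan. The text does not exclude the second.

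**Effect of adjustment.** Let s² be the variance of the between-eye difference in thickness, assumed equal at baseline and follow-up, and r the correlation between the two.
- Variance of the difference in change: 2s²(1 − r).
- Residual variance after regression on the baseline difference: s²(1 − r²).
- Ratio: (1 − r²) / (2(1 − r)) = (1 + r)/2.

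The documents give no value for r, so the table shows a range. The interval column is 1 − √((1+r)/2), before the cost of estimating the slope. Power is for 30 pairs and a 5 micron difference with SD_diff = 8.49, by simulation with t-based tests. It therefore includes the lost degree of freedom and the variance of the estimated slope.

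| r (assumed) | Variance ratio | 95% CI narrower by | Power, adjusted | Power, unadjusted |
|---|---|---|---|---|
| 0.5 | 0.75 | 13% | about 94% | about 88% |
| 0.7 | 0.85 | 8% | about 91 to 92% | about 88% |
| 0.9 | 0.95 | 2.5% | about 88% | about 88% |
| 0.95 | 0.975 | 1.3% | about 87% | about 88% |

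Putting the reduced SD into the t formula with 28 degrees of freedom, without charging for the slope, gives 94.9%, 92.2%, 89.2% and 88.4%. Those figures are slightly too favourable. At r = 0.9 the real gain is under one point. At r = 0.95 the cost of the slope exceeds the gain.

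**Second reading of the SD.** With SD_diff = 6, unadjusted paired-t power at 30 pairs is 99.3%. Adjustment then cannot matter for power, and only the interval width is affected.

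**Eye order.** Coded −0.5/+0.5 with 15 pairs in each order, this term costs one further degree of freedom and changes power by a fraction of a point. Coded 0/1, the intercept becomes the effect in one order only, and power at SD_diff = 8.49 falls to about 60 to 70%.

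**The case against.** **The plan does not choose an unadjusted analysis.** A reader might infer from the endpoint definition that raw change will be compared. Section 5.3.1 defines a variable, however, and Section 5.2 leaves the test open. Regressing change on baseline gives the same treatment estimate as regressing follow-up on baseline, so a change endpoint is compatible with adjustment. This objection stands: adjustment is neither planned nor excluded.

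**Baseline is already used.** The change score subtracts the preoperative scan, and pairing removes between-patient variation. This also stands. The only question is whether the baseline is used as efficiently as it could be.

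**There is no bias.** It is tempting to say that chance imbalance between the eyes distorts the result through regression to the mean. Given a particular observed imbalance, the adjusted and unadjusted estimates do differ. Over the randomisation in Section 3.3.2, the change-score comparison is unbiased, so this restates the precision argument.

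**The trial is not shown to be underpowered for lack of adjustment.** Section 5.1 sizes it on the unadjusted difference in change. At 30 pairs and SD_diff = 8.49, the normal formula gives 89.8% and the paired t 87.7%. The shortfall from 90% comes from rounding and the t distribution.

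**The gain may be nil.** This stands if r is about 0.9 or higher, or, for power, if 6 microns is the between-eye SD.

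What remains is that the covariate is collected, costs almost nothing to use, and is not written into the analysis. Because Section 5.2 is open, the choice between adjusted and unadjusted analysis could also be made after the data are seen.

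**Conclusion.** The point holds as one of efficiency. No baseline-adjusted analysis is pre-specified for the primary endpoint, although the preoperative between-eye difference will be available.

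The gain rests on three assumptions: equal variances at baseline and follow-up, an r that the documents do not give, and the reading of the 6 micron SD. With SD_diff = 8.49 it is worth about 6 points of power at r = 0.5 and 3 to 4 points at r = 0.7. It is immaterial at r = 0.9 and becomes a loss of up to about 1 point at r = 0.95. With SD_diff = 6, power is about 99% or more with or without adjustment. The documents do not support a claim of bias, of inadequate planned power, or of a commitment to unadjusted analysis.

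**What to change.** In Section 5.2, specify the following for each primary time point (Day 15 and Day 30):
- **Outcome:** between-eye difference (test minus control) in change in macular thickness.
- **Covariate 1:** between-eye difference in preoperative thickness, left uncentred so that zero means equal baselines. If it is centred at its sample mean, the intercept returns the unadjusted estimate.
- **Covariate 2:** randomised order, coded −0.5/+0.5.
- **Estimate:** the intercept, reported as the adjusted treatment effect with its 95% CI.

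A mixed model with a patient random effect and a single eye-level baseline slope should not be treated as interchangeable, because that slope blends between-patient and within-patient relations. In a simulation with r = 0.5 and an assumed between-patient SD of 20 microns, its slope averaged 0.98, against 0.52 for the difference regression. The SD of its treatment estimate was 1.49, against 1.50 for the change score and 1.37 for the difference regression. If a mixed model is preferred, give it separate within-patient and between-patient baseline terms.

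The same form can serve the pachymetry change endpoints. The cost is a few lines of text, simple programming and one or two degrees of freedom, with a slight loss only if r is very high. No new data, visits or patients are needed. The model does not settle how the two primary time points share the 5% level, which needs its own rule.
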